2.1. Multiplicity Adjustment

Using a nominal alpha of 2.5% for each of them will ensure the global type I error for the primary objectives is controlled below 2.5%.

3. ANALYSIS SETS

Analysis Set	Definition / Criteria
Enrolled set*	Participants who agreed to participate in a clinical study after completion of the informed consent process.
Safety/Exposed set (ES)	All participants who received a study intervention. Analysis per group is based on the study intervention administered.
Per-Protocol set (PPS)	All eligible participants who received at least one study intervention as per-protocol in the control group and all study interventions in the Co-Ad group , had immunogenicity results pre-post-dose for at least one antigen, complied with blood draw intervals (refer to intervals mentioned below) and contribution of participants to PPS at specific timepoint will be defined by timepoint, without intercurrent medical conditions that may interfere with immunogenicity and without prohibited concomitant medication/vaccination.

*All participants enrolled and included in the database will be part of the enrolled set.

Intervals for the Co-Ad group: Visit1-Visit2=30-37 days

Intervals for the Control group: Visit1-Visit2=30-37 days, Visit2-Visit3=30-37 days

3.1. Criteria for eliminating data from Analysis Sets

Elimination codes will be used to identify participants to be eliminated from analysis. Detail is provided below for each set.

3.1.1. Elimination from Exposed Set (ES)

Code 1030 (Study intervention not administered at all), 800 (Fraudulent data) and code 900 (invalid informed consent) will be used for identifying participants eliminated from ES (see [Table 1](#)).

3.1.2. Elimination from Per-protocol Set (PPS)

A participant will be excluded from the populations for analysis under the following conditions:

- For codes 800, 900, 1030, 1050 and 2020: participants will be eliminated for all visits.
- For codes 1070, 1080, 1090: participants will be eliminated from a specific visit (at which the condition is met) onwards as applicable for the respective group/antigens.
- For codes 1040, 2010, 2040, 2050, 2080: participants will be eliminated from a specific visit (at which the condition is met) onwards.
- 2090, 2100, 2120: participants will be eliminated at the specific visit at which the condition is met.

Table 1 List of elimination codes

Code	Condition under which the code is used	Visit /Contact(timepoints) where the code is checked	Visit from when it is applicable	Applicable for analysis set/endpoint
800	Fraudulent data	All	All	ES and PPS for analysis of immunogenicity
900	Invalid informed consent	All	All	ES and PPS for analysis of immunogenicity
1030	Study intervention not administered at all	All	All	ES and PPS for analysis of immunogenicity
1040	Administration of concomitant vaccine(s) forbidden in the protocol Use of any investigational or non-registered vaccine other than the study interventions during the period beginning 30 days before the first study vaccine administration or planned use during the study period. Planned or actual administration of a vaccine not foreseen by the study protocol in the period starting 30 days	Visit 1,2,3	From the specific visit the condition is met	PPS for analysis of immunogenicity

Code	Condition under which the code is used	Visit /Contact(timepoints) where the code is checked	Visit from when it is applicable	Applicable for analysis set/endpoint
	before the first study intervention administration and ending 30 days after the last study intervention administration. Note: In case an emergency mass vaccination for an unforeseen public health threat (e.g.: a pandemic) is recommended and/or organized by the public health authorities, outside the routine immunization program, the time period described above can be reduced if necessary for that vaccine provided it is used according to the local governmental recommendations and that the Sponsor is notified accordingly.			
1050	Randomisation failure: Subject not randomized in the correct group (To be attributed by Statistician only; Check SBIR, replacement, vaccine administration)	Visit 1	All	PPS for analysis of immunogenicity
1070	Vaccine administration not according to protocol Incomplete vaccination course Participant was vaccinated with the correct vaccine but containing a lower volume Wrong replacement or study vaccine administered (not compatible with the vaccine regimen associated to the treatment number) Route of the study vaccine is not intramuscular Side of administration wrong (for Co-ad group if both vaccines are given in the same arm) Wrong reconstitution of administered vaccine	Vaccination visit(s) 1 or 1 and 2 as applicable	From the specific visit (1 or 2) the condition is met as applicable for the respective group/antigens.	PPS for analysis of immunogenicity
1080	Vaccine temperature deviation Vaccine administered despite a Good Manufacturing Practices (GMP) no-go temperature deviation	Vaccination visit(s) 1 or 1 and 2 as applicable	From the specific visit (1 or 2) the condition is met as applicable for the respective group/antigens.	PPS for analysis of immunogenicity
1090	Expired vaccine administered	Vaccination visit(s) 1 or 1 and 2 as applicable	From the specific visit (1 or 2) the condition is met as applicable for the respective group/antigens.	PPS for analysis of immunogenicity
2010	Protocol violation linked to inclusion/exclusion criteria All inclusion/exclusion criteria defined in the protocol to be checked.	Visit 1,2,3	From the specific visit (1,2 or 3) the condition is met.	PPS for analysis of immunogenicity

Code	Condition under which the code is used	Visit /Contact(timepoints) where the code is checked	Visit from when it is applicable	Applicable for analysis set/endpoint
2020	All Pre-dose results are missing: RSV-A and HI for the FLU vaccine strains	Co-Ad group: Visit 1 Control group: Visit 1 and Visit 2	All	PPS for analysis of immunogenicity
2040	
Administration of any medication forbidden by the protocol
 
Use of any investigational or non-registered product (drug or medical device) other than the study interventions during the period beginning 30 days before the first study vaccine administration or planned use during the study period.
 
Administration of long-acting immune-modifying drugs or planned administration at any time during the study period (e.g. infliximab).
 
Administration of immunoglobulins and/or any blood products or plasma derivatives planned administration during the study period.
 
Chronic administration (defined as more than 14 consecutive days in total) of immunosuppressants or other immune-modifying drugs planned administration during the study period. For corticosteroids, this will mean prednisone ≥ 20 mg/day, or equivalent.
 
Inhaled and topical steroids are allowed.
	Visit 1,2,3	From the specific visit (1,2 or 3) the condition is met	PPS for analysis of immunogenicity
2050	Intercurrent medical condition: Participants may be eliminated from the PPS for immunogenicity if, during the study, they incur a condition that has the capability of altering their immune response (intercurrent medical condition) or are confirmed to have an alteration of their initial immune status.	Visit 1,2,3	From the specific visit (1,2 or 3) the condition is met	PPS for analysis of immunogenicity
2080	Participants did not comply with vaccination schedule for the control group number of days between dose 1 and dose 2 is outside [30-37 days]	Visit 2	Visit 3 for the control group	PPS for analysis of immunogenicity
2090	Participants did not comply with blood sample schedule: Co-Ad group: Number of days between vaccination (visit1) and blood sample (visit2) is outside [30-37] days Control group: Number of days between vaccination (visit1) and blood sample (visit2) or (visit2) and blood sample (visit3) is outside [30-37] days	Visit 2, Visit 3 as applicable for the group	At the specific visit (2 or 3) the condition is met as applicable for the respective group	PPS for analysis of immunogenicity

Code	Condition under which the code is used	Visit /Contact(timepoints) where the code is checked	Visit from when it is applicable	Applicable for analysis set/endpoint
2100	Serological results not available at the post dose time point for all antigens tested at that particular time point.	Visit 2,3	At the specific visit (2 or 3) the condition is met as applicable for the respective group	PPS for analysis of immunogenicity
2120	Obvious incoherence/abnormality or error in laboratory data Unreliable released data as a result of confirmed sample mismatch or confirmed inappropriate sample handling at lab	Visit 2, Visit 3	At the specific visit (2 or 3) the condition is met as applicable for the respective group	PPS for analysis of immunogenicity

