****Visit 1 procedures should preferably be done on the same day. If not, all the visit procedures must be repeated prior to the study intervention administration and recorded in the eCRF when required, excluding the informed consent, the collection of demographic data, and blood sampling if previously taken for this visit. If during Visit 2 the study intervention administration is postponed, all the visit procedures must be repeated prior to the study intervention administration and recorded in the eCRF when required, excluding blood sampling if previously taken for this visit.**

¹ Month 7 = 6 months after administration of RSV investigational vaccine. For this contact multiple formats can be proposed by the study site. Please refer to Section 8.2.2.1 for more details.

² The route for measuring temperature can be oral or axillary. Fever is defined as temperature $\geq 38.0^{\circ}\text{C}/100.4^{\circ}\text{F}$ regardless the location of measurement.

³ Sample collected at Day 1 will be used as baseline for the FLU vaccination in the Control group.

⁴ Sample collected at Day 31 will be used for the post-vaccination FLU vaccine-related testing. This sample will also be used as baseline for the RSV vaccination in the Control group.

⁵ Sample collected at Day 61 will be used for the post-vaccination RSV vaccine-related testing.

⁶ SAEs related to study participation, or to a concurrent GSK medication/vaccine should be collected from the time of consent obtained (prior to study vaccine administration) up to study end.

Table 3 Intervals between study visits (Co-Ad group)

Interval	Planned visit interval	Allowed interval range
Visit 1→Visit 2	30 days	30-37 days
Visit 1→Contact	180 days	180-210 days

Table 4 Intervals between study visits (Control group)

Interval	Planned visit interval	Allowed interval range
Visit 1→Visit 2	30 days	30-37 days
Visit 2→Visit 3	30 days	30-37 days
Visit 2→Contact	180 days	180-210 days

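### SAP 3.1.2 gives code 2080 (Control RSV dose outside 30-37 days) two different starting visits; the bullet should be aligned with Table 1, which applies it from Visit 3

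*SAP*

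**What the plan says.** SAP Section 3.1.2 opens with bullets that group the elimination codes by when they take effect. The one at issue reads: "For codes 1040, 2010, 2040, 2050, 2080: participants will be eliminated from a specific visit (at which the condition is met) onwards". The bullet just above it, for dosing-error codes 1070, 1080 and 1090, has a limit that this one lacks: "onwards as applicable for the respective group/antigens".

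Table 1, in the same section, then gives a row per code. One column names the visit where the code is checked. Another, headed "Visit from when it is applicable", names where elimination begins. For code 2080 the row gives:

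- the trigger, for the Control group: "number of days between dose 1 and dose 2 is outside [30-37 days"
- the visit where it is checked: Visit 2
- the starting visit: "Visit 3 for the control group"

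Blood-draw timing has its own code, 2090 ("Participants did not comply with blood sample schedule"), which removes only the affected visit. SAP Section 3 defines the PPS visit by visit: "contribution of participants to PPS at specific timepoint will be defined by timepoint".

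**The concern.** In the Control group, dose 2 is the RSV vaccine at Visit 2. A dosing interval outside the window is therefore a Visit 2 condition, and the bullet read plainly removes the participant from Visit 2 onwards. Table 1 removes the same participant from Visit 3 onwards.

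Visit 2 is where the HI primary endpoint is read in both groups (SAP 4.2.1). In Controls that sample also serves as the pre-RSV baseline (Protocol 1.3, Table 2 footnotes). Blood taken before the RSV dose cannot be affected by that dose being late, so there is no scientific reason to discard its HI results.

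At stake is which Control participants enter four of the six primary comparisons. Code 2080 can only apply to Controls. The bullet's reading would therefore drop HI results in one arm for a reason that cannot arise in the Co-Ad group.

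**Working it through.** **1. Compare the bullet with Table 1, code by code.** The rows for 1040, 2010, 2040 and 2050 all start elimination at the visit where the condition is met, as the bullet says. Only 2080 differs: Visit 2 by the bullet, Visit 3 by its row. Both are current SAP text.

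**2. Can an in-window sample go with a late dose?** Yes, under the protocol's own rules. If the Visit 2 dose is postponed, the Table 2 footnote in Protocol 1.3 has the visit procedures repeated, "excluding blood sampling if previously taken for this visit". Protocol 5.5 defers dosing to at least 14 days after a known COVID-19 contact, and the visit window is 37 − 30 = 7 days wide. A contact 24 days after Visit 1 puts the earliest dose at 24 + 14 = 38 days, past the limit of 37. If blood was drawn on days 30-37, code 2090 is not triggered and only 2080 applies.

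**3. Reproduce the plan's power.** Inputs from SAP Section 5, Table 2: 462 per group, one-sided alpha 2.5%, margin 1.5, true ratio 1.05, log10 SD 0.6 (HI) and 0.45 (RSV).

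- Distance to margin: log10(1.5) − log10(1.05) = 0.1761 − 0.0212 = 0.1549
- HI standard error: 0.6 × √(2/462) = 0.03948; noncentrality 0.1549/0.03948 = 3.92; noncentral-t power 97.50% (plan: 97.5%)
- RSV standard error: 0.45 × √(2/462) = 0.02961; noncentrality 5.23; power 99.946% (plan: 99.9%)
- Global power: 89.89% as one minus the summed type II errors; 0.97499⁴ × 0.99946² = 90.27% as a product under independence (plan: about 90%)

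**4. Compare the two readings.** The documents give no rate of late dosing after in-window blood, so the shares below are assumptions. Co-Ad stays at 462. Under Table 1 only the Control RSV comparisons lose participants; under the bullet the HI comparisons lose them too. Joint power is HI⁴ × RSV².

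| Assumed Control loss | Control n | HI power per strain at this n | RSV power at this n | Joint, Table 1 | Joint, bullet | Gap (points) |
|---|---|---|---|---|---|---|
| 1% | 457 | 97.44% | 99.943% | 90.26% | 90.03% | 0.2 |
| 3% | 448 | 97.32% | 99.937% | 90.25% | 89.58% | 0.7 |
| 5% | 439 | 97.19% | 99.931% | 90.24% | 89.10% | 1.1 |
| 10% | 416 | 96.82% | 99.912% | 90.21% | 87.73% | 2.5 |

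The Table 1 column keeps HI at n = 462 (97.50% per strain). All rows describe losses beyond the planned allowance of 514 − 462 = 52 non-evaluable participants per group. Within that allowance, planned power holds under either reading.

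**5. One-arm shift.** Suppose the dropped 5% of Controls had HI titers half those of the rest (an assumption). Removing them would raise the unadjusted Control GMT, and so the Control/Co-Ad ratio, by 10^(0.05 × log10 2) = 1.035, against a margin of 1.5. If their titers were twice as high, the ratio would fall by the same factor.

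**The case against.** The strongest reply is that the SAP settles the matter itself. Table 1 belongs to the same section, has a separate column for the starting visit, and fills it for 2080. A specific row would normally govern a bullet that covers five codes. The checking visit and the starting visit are also distinct columns, and in the case at issue the late interval arises after the Day 31 blood draw, so the bullet can be stretched to agree with the table. What stands is that a programmer working from Table 1 gets the right set. What does not stand is that the bullet is harmless wording: it states an operative rule for the primary analysis set, and on its ordinary meaning the rule is wrong for this code.

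The scenario is also narrow. Protocol 8.2.1.4 reschedules the visit when health on the day precludes dosing. Protocol 8.2.1.6 reschedules it within the allowed interval for fever. If the whole visit slips past day 37, code 2090 removes the HI result under either reading. The COVID-19 contact example needs a site that draws blood in window while deferring the dose. That stands, and it limits how many participants could be affected.

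A reader might also infer that Protocol Section 8 must change. It allows a further 30 days for the Control RSV dose in special circumstances and leaves the effect on the PPS to case-by-case judgement, while code 2080 has no exception. The documents do not support that demand. The provision is deliberate, and the mismatch within SAP 3.1.2 can be removed without touching it.

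**Conclusion.** Wrong as written, and minor. SAP 3.1.2 gives two starting visits for code 2080, and Table 1 has the correct one. Confidence is high on the mismatch and on which rule is right. Any consequence for the results is conditional on the bullet being the text that is programmed.

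Even then the effect is small: 0.2 to 2.5 points of joint power for assumed losses of 1% to 10% of evaluable Controls. Those figures rest on the plan's SDs and true ratio, on independence between endpoints, and on losses beyond the 10% allowance.

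Two stronger readings are tempting, and neither is supported. One is that the plan discards valid HI results: it does so only if Table 1 is ignored. The other is that the non-inferiority conclusion is biased: the documents give neither a rate of late dosing nor a reason for affected Controls to have unusual titers, and the illustrative shift of 1.035 is far from the margin. The testing laboratory is blinded (Protocol 6.3.5), and SAP 4.2 adds an ES analysis if exclusions reach 5% in any group.

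**What to change.** In SAP 3.1.2, remove 2080 from the bullet it shares with 1040, 2010, 2040 and 2050. Give it its own line stating that it eliminates Control participants from Visit 3 onwards, as in Table 1. No antigen limit needs adding: some Visit 3 read-outs in Protocol Table 11 are redacted, and the Visit 3 start already protects the Day 31 HI results. Table 1 and the protocol, including Section 8, stay as they are.

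The cost is one code moved and one line added in the SAP. No data, margin, sample size or test changes. It should be done before the PPS is programmed, so that the choice is not left to that stage.

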4. STATISTICAL ANALYSES

4.1. General Considerations

4.1.1. General Methodology

95% CI for proportion will be based on exact Clopper-Pearson confidence interval [[Clopper](#), 1934].

95% CI for group difference in proportion will be based on Miettinen and Nurminen confidence interval [[Miettinen](#), 1985].

The group adjusted GMT ratio will be based on a back transformation of group contrast in an ANCOVA model applied to the logarithm- transformed titers.

Primary Analysis: The ANCOVA model will include the treatment group and age category (age at vaccination: 65-69, 70-79 or ≥ 80 years) as fixed effects and the pre-dose log-10 titer as regressors.

Sensitivity Analysis: The ANCOVA model will include the treatment group and age category (age at vaccination: 65-69, 70-79 or ≥ 80 years) as fixed effects, center as the random effect and the pre-dose log-10 titer as regressors.

95% CI for GMT will be based on a back transformation of student CI for the mean of log-transformation.

4.1.2. Definitions

- For the RSV antigens:

A seronegative participant will be defined as a participant whose antibody titer/concentration is below the cut-off value of the assay. A seropositive participant is a participant whose antibody titer/concentration is greater than or equal to the cut-off value of the assay.

MGI (mean geometric increase): The geometric mean of the within participant ratios of the post-dose titer over the pre-dose titer.

- For the FLU antigens:

SCR (seroconversion rate): The percentage of vaccinees who have either a HI pre-dose titer $< 1:10$ and a post-dose titer $\geq 1:40$ or a pre-dose titer $\geq 1:10$ and at least a four-fold increase in post-dose titer.

HI SPR (seroprotection rate): The percentage of vaccinees with a serum HI titer $\geq 1:40$ that usually is accepted as indicating protection.

MGI (mean geometric increase): The geometric mean of the within participant ratios of the post-dose titer over the pre-dose titer.

4.2. Primary Endpoints Analyses

The primary analysis will be based on the PPS for analysis of immunogenicity. If, in any vaccine group, the percentage of vaccinated participants with serological results excluded from the PPS for analysis of immunogenicity is 5% or more, a second analysis based on the ES will be performed to complement the PPS analysis.

4.2.1. Between groups assessment

- The 2-sided 95% CI for the group GMT ratio in terms of RSV-A neutralizing antibody titers between RSVPreF3 OA investigational vaccine administered alone (Control group) over RSVPreF3 OA investigational vaccine when co-administered with the FLU vaccine (Co-Ad group) will be computed at 1 month after the RSVPreF3 OA investigational vaccine dose (i.e. at Day 31 [Visit 2] for the Co-Ad group and at Day 61 [Visit 3] for the Control group).
- The 2-sided 95% CI for the group GMT ratio in terms of HI antibody titers for each of the FLU vaccine strains between RSVPreF3 OA investigational vaccine administered alone (Control group) over RSVPreF3 OA investigational vaccine when co-administered with the FLU vaccine (Co-Ad group) will be computed at 1 month after the FLU vaccine (i.e. at Day 31 [Visit 2] for both groups):
- The 2-sided 95% CI for the group GMT ratio in terms of RSV-B neutralizing antibody titers between RSVPreF3 OA investigational vaccine administered alone (Control group) over RSVPreF3 OA investigational vaccine when co-administered with the FLU vaccine (Co-Ad group) will be computed at 1 month after the RSVPreF3 OA investigational vaccine dose (i.e. at Day 31 [Visit 2] for the Co-Ad group and at Day 61 [Visit 3] for the Control group).

The results will be presented in tables as well as graphs using forest plots.

4.2.2. Main analytical approach

The 2-sided 95% CI for group adjusted GMT ratio will be derived from an ANCOVA model* on \log_{10} transformed titer.

***Primary Analysis:** The model will include the treatment group and age category (age at vaccination: 65-69, 70-79 or ≥ 80 years) as fixed effects, and the pre-dose \log_{10} -transformed titer as covariate. Missing data will not be replaced. Titers below the assay cut-off will be replaced by half the assay cut-off, titers above the upper limit of quantification (ULOQ) will be replaced by the ULOQ.

Success criteria for non-inferiority and testing sequence:

The following testing sequence will be used:

1st sequence:

- The upper limit of the 2-sided 95% CI of the GMT ratio (Control group divided by Co-Ad group) for RSV-A neutralization antibodies is ≤ 1.5 .

AND

- The upper limit of the 2-sided 95% CI of the GMT ratio (Control group divided by Co-Ad group) for each of the FLU vaccine strains are ≤ 1.5 .

2nd sequence:

- The upper limit of the 2-sided 95% CI of the GMT ratio (Control group divided by Co-Ad group) for RSV-B neutralization antibodies is ≤ 1.5 .

Testing will progress in the 2nd sequence only if the 1st sequence is a success, so that no further adjustment of alpha is required.

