6.3.3. Intervention allocation to the participant

An automated Internet-based system, Source data Base for Internet Randomization (SBIR) will be used for randomization and for identification of intervention material. The randomization algorithm will use a minimization procedure accounting for age (65-69, 70-79 or ≥ 80 years) and center. Minimization factors will have equal weight in the minimization algorithm. Refer to Section 4.1.2 for the enrolment rules.

Once a participant identification number is allocated, the randomization system will determine study group and will provide the study intervention number to be used for the first dose. The study intervention number(s) to be used for subsequent dosing will be provided by the same automated Internet-based system (SBIR).

When SBIR is not available, please refer to the SBIR user guide or SPM for specific instructions.

Refer to the SPM for additional information relative to the intervention number allocation.

**6.3.4. Allocation of participants to assay subsets (amended
16 December 2022)**

Not applicable for this study.

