4.2.3. Sensitivity analyses

As for the main analytical approach an ANCOVA model will be performed with the treatment group and age category (age at vaccination: 65-69, 70-79 or ≥ 80 years) as fixed effects, **center as random effect** and the pre-dose \log_{10} -transformed titer as covariate.

In case the model with random effect does not converge we proceed with center as a fixed effect.

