5. SAMPLE SIZE DETERMINATION

The target enrolment will be 1028 participants (514 in the group receiving the RSVPreF3 OA investigational vaccine co-administered with the FLU vaccine (Co-Ad group) and 514 in the Control group where RSVPreF3 OA investigational vaccine and FLU vaccine are administered staggered) to obtain at least 924 evaluable participants (462 in the Co-Ad group and 462 in Control group) for the evaluation of the primary objectives, assuming that approximately 10% of the enrolled participants will not be evaluable.

Each objective will be evaluated with a nominal type I error of 2.5%.

Table 2 Overall power to demonstrate primary objectives: non-inferiority of the immunogenicity of RSVPreF3 OA investigational vaccine when co-administered with FLU vaccine as compared to when administered alone- assuming 462 participants are available in each group

Endpoint	Standard deviation of log ₁₀ concentration	Reference ratio	Non-inferiority margin	Type II error	Power
RSV-A Non-inferiority* (1-sided test with alpha = 2.5%)					
GMTs RSV-A neutralization antibody	0.45	1.05	1.5	0.1%	99.9%
FLU Non-inferiority* (1-sided test with alpha=2.5%)					
GMTs HI H1N1 strain	0.6	1.05	1.5	2.5%	97.5%
GMTs HI H3N2 strain	0.6	1.05	1.5	2.5%	97.5%
GMTs HI B/Yamagata	0.6	1.05	1.5	2.5%	97.5%
GMTs HI B/Victoria strain	0.6	1.05	1.5	2.5%	97.5%
RSV-B Non-inferiority* (1-sided test with alpha = 2.5%)					
GMTs RSV-B neutralization antibody	0.45	1.05	1.5	0.1%	99.9%
Global Type II error to show non-inferiority					~10.0%
Global power					~90.0%

* Pass 2019 alpha = 2.5%, Two-Sample T-Tests for Non-Inferiority Assuming Equal Variance and Equal mean

For RSV: non-inferiority limit = 0.176 (=log₁₀[1.5]).

For each Flu vaccine strain: non-inferiority limit = 0.176 (=log₁₀[1.5]).

Reference Ratio= 0.0212 (=log₁₀[1.05])

Considering a slight interference of 1.05 in true GMTs in both groups with a common population standard error of 0.45 for the RSV-A and RSV-B neutralization antibodies and 0.6 for each of the FLU strains in log₁₀ transformed concentration, the study has at least 90.0% power to meet the primary objectives.

Nominal powers to evaluate secondary objective

The nominal power to evaluate the non-inferiority on seroconversion rate for each of the FLU strains is above 86%, depending on the plausible rates.

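### Center is a minimization factor but is left out of the confirmatory ANCOVA, so the deciding confidence intervals are slightly too wide if centers differ after age and baseline adjustment

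*SAP*

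**What the plan says.** Protocol 6.3.3 describes the allocation: "The randomization algorithm will use a minimization procedure accounting for age" category and center. It adds: "Minimization factors will have equal weight in the minimization algorithm".

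For the confirmatory analysis, SAP 4.2.2 states: "The model will include the treatment group and age category", with pre-dose log10 titer as covariate. SAP 4.1.1 gives the same primary model, with treatment and age category "as fixed effects and the pre-dose log-10 titer as regressors", and Protocol 9.4.1 agrees. None of the three includes center.

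Center enters only in the sensitivity model, which has "center as the random effect and the pre-dose log-10 titer as regressors" (SAP 4.1.1). SAP 4.2.3 adds a fallback: "In case the model with random effect does not converge we proceed with center as a fixed effect". The success rule in SAP 4.2.2 compares the upper 95% limit from the primary model with 1.5 and gives the sensitivity model no role. RSV-A and all four HI strains must pass before RSV-B is tested.

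**The concern.** One of the two allocation factors is modelled and the other is not, without explanation. Center differences carried by age or pre-dose titer are already removed by the covariates. Minimization spreads most of what remains evenly over the two groups, so it hardly moves the treatment contrast. A model without center nevertheless leaves that variation in the residual, and its standard error then exceeds the true one.

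What is at stake is efficiency, not validity. The upper confidence limit is the decision rule, and a narrow miss on one HI strain fails the first sequence and blocks the RSV-B test. The HI strains also carry nearly all the planned type II error: 4 × 2.5 = 10.0 of the 4 × 2.5 + 2 × 0.1 = 10.2 summed points.

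**Working it through.** **Inputs from SAP 5.** 462 evaluable per group; margin log10(1.5) = 0.1761; true ratio 1.05, log10 = 0.0212; SD 0.6 for each HI strain and 0.45 for RSV-A and RSV-B; one-sided alpha 2.5%. The distance to the margin is d = 0.1761 − 0.0212 = 0.1549.

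**The plan's own figures.** The stated method is "Two-Sample T-Tests for Non-Inferiority Assuming Equal Variance and Equal mean". For SD 0.6, SE = 0.6 × √(2/462) = 0.03948, and the noncentral t gives 97.50% power (plan: 97.5%). For SD 0.45 it gives 99.95% (plan: 99.9%). Global power is 89.9% by summing type II errors or 90.3% by multiplying powers (plan: about 90%). These figures involve no covariates and no center term, so they do not depend on this point.

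**Assumptions.** The documents give neither of the next two quantities:
- s: the share of variance left after age and pre-dose titer that lies between centers, taken as 2%, 5% or 10%.
- R2: the share of total variance that age and pre-dose titer explain, taken as 0 to 0.3.

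**Formulas**, assuming balance within centers:
- Model SE without center = 0.6 × √(1 − R2) × √(2/462); true SE = that × √(1 − s).
- One-sided error without center = Φ(−t/√(1 − s)), with t = 1.9625.
- Largest observed ratio that passes = 10^(0.1761 − t × SE).
- Power without center = Φ((d − t × SE)/(SE × √(1 − s))); power with center from the noncentral t, assuming 40 centers.

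Example, R2 = 0 and s = 5%: √0.95 = 0.9747. The largest passing ratio is 10^(0.1761 − 1.9625 × 0.03948) = 1.255 without center and 10^(0.1761 − 1.9625 × 0.03948 × 0.9747) = 1.261 with it. Power without center is Φ((0.1549 − 0.0775)/0.0385) = 97.79%.

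| Center share s | Interval narrower by | One-sided error without center | Largest passing HI ratio, R2 = 0 (1.255 without center) | Same, R2 = 0.3 (1.292 without center) |
|---|---|---|---|---|
| 2% | 1.0% | 2.37% | 1.257 | 1.294 |
| 5% | 2.5% | 2.20% | 1.261 | 1.297 |
| 10% | 5.1% | 1.93% | 1.266 | 1.302 |

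| R2 | s | HI power, without → with center | Global bound (1 − summed type II error), without → with |
|---|---|---|---|
| 0 | 2% | 97.62% → 97.72% | 90.4% → 90.8% |
| 0 | 5% | 97.79% → 98.04% | 91.1% → 92.1% |
| 0 | 10% | 98.07% → 98.51% | 92.2% → 94.0% |
| 0.3 | 2% | 99.71% → 99.72% | 98.8% → 98.9% |
| 0.3 | 5% | 99.74% → 99.78% | 99.0% → 99.1% |
| 0.3 | 10% | 99.80% → 99.86% | 99.2% → 99.4% |

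At s = 2%, 5% and 10%, the global bound gains 0.3, 0.6 and 1.1 points for R2 = 0.1, and 0.1, 0.3 and 0.6 points for R2 = 0.2. RSV-A and RSV-B power is at least 99.9% in every case.

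**Simulation.** Minimization on age and center was simulated with 20 or 60 centers and a 0.9 probability of the preferred arm (both assumed), center as a fixed effect, 4000 runs per setting. Without center, the one-sided error was 2.0–2.1% at s = 5% and 1.8–2.0% at s = 10%; with center it was 2.3–2.4%. The ratio of interval widths was 0.977–0.980 and 0.952–0.955. With center as a random effect (1000 runs per setting), the standard error was 2 to 5% smaller at s = 5 to 10%, no precision was visibly lost at s = 0, and the error rate was within simulation noise of nominal. A separate run of 3000 per setting agreed in direction, except for one setting (40 centers, s = 5%) that gave 2.8% without center. The model with center gave 2.9% in those same runs, so this is probably shared noise.

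**The case against.** The strongest reply is that nothing here is an error. The center model is pre-specified and will be reported beside the primary one, the Protocol and SAP agree, and the present model is safe. In every scenario above, HI power without center exceeds the planned 97.5% and the global bound exceeds 90%. Residual center variance may well be small: titers are measured in sponsor-designated laboratories blinded to group, everyone receives the same two vaccines, and age and baseline are already adjusted for. The passing ratio moves by only 0.002 to 0.011, while GMT ratios are displayed to two decimals. Promoting the center model also brings a random-else-fixed switch into the decision, and changing the decision model of an open-label trial after a SAP amendment carries a credibility cost.

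Most of this is right about size, and it keeps the point minor. It does not remove it. A sensitivity analysis outside the success rule cannot change the interval that decides non-inferiority, and if the two models fell on opposite sides of 1.5, the SAP offers no rationale for preferring the one without an allocation factor. The reliance on the fallback is a real drawback and has to be settled in the wording. The credibility cost is why any change must come before group-level results are seen.

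**Conclusion.** The concern holds, as a modest efficiency point to consider. Center is an allocation factor missing from the decision model. If centers differ after age and baseline adjustment, the intervals are too wide and the true one-sided error falls below 2.5%: to about 2.4%, 2.2% or 1.9% at residual center shares of 2%, 5% or 10%. A false non-inferiority claim cannot arise from this.

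The gain lies in the four HI strains; RSV-A and RSV-B gain almost nothing. The 1.8-point maximum needs both a 10% residual center share and no variance explained by age or baseline. The size rests on assumed values for the center share, R2, the number of centers and the minimization probability, and the analytic figures assume balance within centers. The direction does not depend on the exact values, provided some center variance remains and the minimization balances it.

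**What to change.** Before group-level results are seen, make the specified center model the primary ANCOVA: treatment, age category, pre-dose log10 titer, and center as a random effect with the fixed-effect fallback. Use it for all six endpoints for consistency, and keep the model without center as the sensitivity analysis. State that a random-effect variance estimated at zero counts as converged, so that the fallback applies only to true non-convergence, and name the degrees-of-freedom method for the mixed model. If the sponsor prefers the present order, a sentence explaining why center is left out of the decision model is enough.

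The cost is an amendment to SAP 4.1.1, 4.2.2 and 4.2.3 and Protocol 9.4.1; both models are already planned. The downside is that different strains could be decided by different forms of the model, and many small centers cost some precision. If centers explain nothing and the fixed-effect form is used, the simulated standard error rises by about 0.1% with 20 centers and 0.5% with 60 (numbers of centers assumed).
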